***For the following conditions in Expansion Cohorts 1-8, the sponsor medical officer's approval of enrolment is needed:***

- if documented progression has not been on measurable disease (i.e. symptomatic progression)

2. Patients must have measurable disease according to RECIST (Response Evaluation Criteria In Solid Tumors) version 1.1.

- A minimum of one lesion  $\geq 10$  mm (or twice the slice thickness if slices are not 5 mm thick) in the longest diameter (LD) from a non-irradiated area
  - Lymph nodes lesion  $\geq 15$  mm in the shortest diameter from a non-irradiated area
  - If target lesion(s) are located within previously irradiated area patients can be enrolled if:
    - target lesions have not been irradiated within the last 3 months
    - there has been demonstrated progression in the "in field" target lesion and after sponsor acceptance
- In the dose escalation part, patients with ovarian cancer can be included based on CA 125 positivity according to the Gynecologic Cancer Intergroup Guideline; only if they have a pretreatment sample that is at least twice the upper limit of the reference range and within 2 weeks before starting the treatment.

Note: Patients are not evaluable by CA 125 if they have received mouse antibodies (unless the assay used has been shown not to be influenced by human anti-mouse antibody) or if there has been medical and/or surgical interference with their peritoneum or pleura during the previous 28 days (e.g., paracentesis).

3. A) In the dose escalation part all patients must provide a tumor tissue sample (Formalin Fixed Paraffin Embedded (FFPE) blocks / slides) from archival tissue or fresh biopsy

Document Name: GCT1021-01 Protocol

Document Number: TMF-03326

Version: 11.0

collected before Cycle 1 Visit 1, preferably derived from advanced disease stage. B) In the expansion part all patients must provide a mandatory fresh biopsy (FFPE tissue blocks/slides) at screening (aspirates are not acceptable) which contains tumor tissue and is taken after failure/stop of last prior treatment. Documentation of the fresh FFPE biopsy shipment must be submitted to the Sponsor as a part of eligibility package prior to administration of first dose of enapotamab vedotin. In case it is not feasible to meet the required criteria for a fresh tumor biopsy, the sponsor medical officer's approval of enrollment is needed. Furthermore the latest available archival tumor tissue sample should be collected if available.

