#### 8.4.7 Imaging/Computed Tomography

All patients will have a CT-scan with contrast of thorax, abdomen and pelvis performed during screening. If there is suspicion of brain metastases/tumors, a CT-scan of the head will be performed before inclusion. For patients with stable brain metastases enrolled in the expansion part, the CT-scan must include the head and neck.

For patients with superficial cutaneous lesions that are not measurable by a CT-scan, measurement using calipers can be performed, using photographs as documentation.

All sites of metastatic disease should be reported at baseline and followed throughout the trial. Up to 5 target lesions (maximum two per organ) will be defined at screening. A lesion from which a fresh biopsy has been taken during the trial cannot be a target lesion.

Baseline imaging assessments will be performed during the screening period. Any imaging assessments already completed for regular radiographic evaluation of the patient's cancer can be considered as the baseline images for this trial, as long as they are of sufficient diagnostic quality and have been obtained ≤ 28 days prior to C1D1.

Post-baseline scans will be performed every 6 weeks (1Q3W and Cohort 8 3Q4W) or 8 weeks (Cohort 6 3Q4W) (±7 days) from C1D1 until investigator assessed disease progression according to RECIST v1.1. Time points for radiographic evaluation should be calendar based and do not depend on cycle visits i.e. radiological evaluation should be performed regardless of IMP administration delays. For patients who permanently discontinue IMP for other reasons than disease progression (e.g., adverse events), every effort should be made to continue on-trial radiological evaluation according to protocol until disease progression, start of a new anti-cancer treatment, withdrawal of consent or death (see [Table 11](#)).

Document Name: GCT1021-01 Protocol

Document Number: TMF-03326

Version: 11.0

---

If reduction of target lesions  $\geq 30\%$  in size is observed a repeat CT-scan will be performed after 4 (in particular for the 3Q4W-arm) to 6 weeks (in particular for the 1Q3W-arm) to confirm the response.

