**Table 26. Definition of Response (RECIST Criteria v1.1)**

	Category	Criteria
Based on target lesions	Complete Response (CR)	Disappearance of all target lesions. Any pathological lymph nodes must have reduction in short axis to < 10 mm.
	Partial Response (PR)	≥ 30% decrease in the sum of the LD of target lesions, taking as reference the baseline sum LD.
	Stable Disease (SD)	Neither sufficient shrinkage to qualify for PR nor sufficient increase to qualify for PD, taking as reference the smallest sum of LDs since the treatment started.
	Progressive Disease (PD)	≥ 20% increase in the sum of the LDs of target lesions, taking as reference the smallest sum of the LDs recorded since the treatment started or the appearance of one or more new lesions.
Based on non-target lesions	CR	Disappearance of all non-target lesions and normalization of tumor marker level. All lymph nodes must be non-pathological in size (< 10 mm short axis).
	SD	Persistence of one or more non-target lesion(s) or/and maintenance of tumor marker level above the normal limits.
	PD	Appearance of one or more new lesions and/or unequivocal progression of existing non-target lesions.

Evaluation of best overall response (RECIST Criteria v1.1)

The best overall response is the best response recorded from the start of the treatment until disease progression/recurrence (taking as reference for PD the smallest measurements recorded since the treatment started).

Patients with a global deterioration of health status requiring discontinuation of treatment without objective evidence of PD at that time should be classified as having “symptomatic deterioration”. Every effort should be made to document the objective progression even after discontinuation of treatment.

Document Name: GCT1021-01 Protocol

Document Number: TMF-03326

Version: 11.0

---

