### Confirmation

PR and CR: changes in tumor measurements that are confirmed by repeat assessments performed no less than 4 weeks after the criteria for response are first met are called confirmed responses. Onset of PR or CR without such confirmation is called unconfirmed.

SD: follow-up measurements must have met the SD criteria at least once and for a minimum time period of 6 weeks ( $\pm 7$  days) after first treatment.

Patients with ovarian cancer will also be evaluated according to CA 125.

A CA 125 response is defined as at least a 50% reduction in CA 125 levels from a pretreatment sample. The response must be confirmed and maintained for at least 28 days. Patients can be evaluated according to CA 125 only if they have a pretreatment sample that is at least twice the upper limit of the reference range and within 2 weeks before starting the treatment.

To calculate CA 125 responses accurately, the following rules apply:

Intervening samples and the 28-day confirmatory sample must be less than or equal to (within an assay variability of 10%) the previous sample.

Variations within the reference range of CA 125 levels will not interfere with the response definition.

For each patient, the same assay method must be used, and the assay must be tested in a quality control scheme.

Patients are not evaluable by CA 125 if they have received mouse antibodies or if there has been medical and/or surgical interference with their peritoneum or pleura during the previous 28 days (e.g., paracentesis).

The date when the CA 125 level is first reduced by 50% is the date of the CA 125 response. To calculate response, an analysis should be used that includes all patients with an initial CA 125 level of at least twice the upper limit of the reference range as eligible and evaluable. In addition, as a separate analysis, those patients who have a CA 125 response and whose CA 125 level falls to within the reference range can be classified as CA 125 complete responders. Patients who have a fall of CA 125 to within the reference range but whose initial CA 125 was less than twice the upper limit of the reference range have not had a CA 125 response and cannot therefore be classified as a CA 125 complete responder.

CA 125 will be presented graphically in plots.

Document Name: GCT1021-01 Protocol

Document Number: TMF-03326

Version: 11.0

---

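### The measurable-lesion rule, read literally, drops below 10 mm for CT slices thinner than 5 mm and states no floor; the effect is unknown and may be nil, and would fall mainly on progression and unconfirmed response

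*Protocol*

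**What the plan says.** Criterion 2 opens with a general requirement: "Patients must have measurable disease according to RECIST (Response Evaluation Criteria In Solid Tumors) version 1.1". The size rule follows as a sub-bullet. It asks for "A minimum of one lesion" of 10 mm or more, "or twice the slice thickness if slices are not 5 mm thick) in the longest diameter (LD) from a non-irradiated area". Section 6.1 carries the same wording, so this is not a slip confined to the Synopsis.

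Protocol Section 8.4.7 governs imaging. It gives no slice thickness and no minimum size for a target lesion. It says "Up to 5 target lesions (maximum two per organ) will be defined at screening", and also "A lesion from which a fresh biopsy has been taken during the trial cannot be a target lesion".

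Table 26 reads response and progression from percentages. Partial response is a 30% or greater "decrease in the sum of the LD of target lesions, taking as reference the baseline sum LD". Progression is a 20% or greater "increase in the sum of the LDs of target lesions, taking as reference the smallest sum of the LDs recorded since the treatment started", or a new lesion. The table gives no minimum change in millimetres. Responses count as confirmed when "confirmed by repeat assessments performed no less than 4 weeks after the criteria for response are first met are called confirmed responses"; progression has no matching requirement.

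Protocol Section 10.2.3 tests response against 10% (15% in Cohort 7), for confirmed and for unconfirmed response. Section 10.4.1 makes confirmed response the main presentation. SAP Section 15.1.1 analyses investigator reads and only lists the independent committee's best responses.

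**The concern.** Ten millimetres is already twice 5 mm. A clause meant to raise the limit for thick slices needs to say *thicker than 5 mm*. As worded it also lowers the limit for thin slices, without a stop. A site screening a patient would apply the size rule in the sub-bullet, and nothing elsewhere in the Protocol or SAP puts 10 mm back as a floor.

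The smaller the sole target, the smaller the absolute change that crosses a percentage threshold. On one 5 mm lesion, 1.5 mm is a partial response and 1.0 mm is progression. Progression is the more exposed outcome: it needs no confirmation, it is taken from investigator reads, Table 26 sets no millimetre minimum, and it is a reason for withdrawal from treatment (Protocol Section 6.3.1). A false call would therefore reach both PFS and the patient's time on treatment. Unconfirmed response is exposed in the same way, but confirmed response much less so.

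**Working it through.** **Inputs from the documents.** Factor 2 × slice thickness and the 10 mm figure (criterion 2); 30% and 20% thresholds (Table 26); one lesion sufficient (criterion 2).

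**Inputs assumed.** Slice thickness 1 to 5 mm; reader SD σ of 0.5, 1.0 or 1.5 mm, independent at each scan; one target lesion with no true change. The documents give none of these.

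**Step 1: the stated figure.** 2 × 5 mm = 10 mm, which agrees with the criterion.

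**Step 2: the literal minimum for other slices, and the change that crosses each threshold.**

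| Slice (mm) | Minimum lesion (mm) | PR needs (30%) | PD needs (20%) |
|---|---|---|---|
| 1 | 2 | 0.6 mm | 0.4 mm |
| 2.5 | 5 | 1.5 mm | 1.0 mm |
| 3 | 6 | 1.8 mm | 1.2 mm |
| 5 | 10 | 3.0 mm | 2.0 mm |

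**Step 3: false calls for an unchanged lesion of size L.** Let the baseline b and follow-up f be independent N(L, σ²).

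- False PR at one scan: P(f ≤ 0.7b) = Φ(−0.3L / (σ√(1 + 0.7²))) = Φ(−0.3L / 1.221σ).
- False PD at one scan: P(f ≥ 1.2b) = Φ(−0.2L / (σ√(1 + 1.2²))) = Φ(−0.2L / 1.562σ).
- False PR at two successive scans: the bivariate normal probability with the PR bound on both scans and correlation 0.49/1.49 = 0.33, since both share one baseline.

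With σ = 1 mm:

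- L = 5: PR Φ(−1.5/1.221) = Φ(−1.229) = 11.0%; PD Φ(−1.0/1.562) = Φ(−0.640) = 26.1%.
- L = 10: PR Φ(−3.0/1.221) = Φ(−2.458) = 0.7%; PD Φ(−2.0/1.562) = Φ(−1.280) = 10.0%.

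Over the assumed range of σ (0.5 / 1.0 / 1.5 mm):

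| Unchanged sole target | False PR, one scan | False PR, repeated | False PD, one scan |
|---|---|---|---|
| 5 mm | 0.7% / 11% / 21% | 0.0% / 2.7% / 7% | 10% / 26% / 33% |
| 10 mm | 0.0% / 0.7% / 5% | 0.0% / 0.0% / 0.8% | 0.5% / 10% / 20% |

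Simulation with 1,000,000 draws agrees with these values.

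**Step 4: dependence on the error model.** Only L/σ enters the formulas. A 5 mm lesion with σ = 0.5 mm gives 0.7% and 10%, the same as a 10 mm lesion with σ = 1.0 mm. If halving the slice also halves the error, there is no excess.

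**Step 5: from patient to cohort.** If a share w of a cohort has a sole 5 mm target, the excess in unconfirmed response at σ = 1 mm is w × (11.0% − 0.7%). With w = 0 it is nil. With w = 5% (illustrative) it is 0.05 × 10.3% = 0.5 percentage points. The documents do not give w.

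**The case against.** Several objections have force.

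- *The governing sentence requires RECIST 1.1.* Response is also assessed under that standard, and Table 26 is a summary of it. The standard's own text is not in the documents, so whether it would override the sub-bullet, or add a millimetre minimum for progression, cannot be settled from them. This limits the claim but does not cure the wording: the sub-bullet is the operative size rule and should agree with the sentence above it.
- *A constant ratio of lesion size to slice thickness is a coherent rule.* This stands as a possible reading. Under proportional error it carries no penalty (Step 4), so the excess in Step 3 depends on holding the SD equal at both sizes.
- *Slice thickness may be set elsewhere.* The SAP refers to an imaging charter, which is not supplied. The 2.5 mm slice is therefore an assumption.
- *Confirmation and multiple lesions protect the response endpoint.* They do. At an SD of 1 mm, confirmation takes the 5 mm figure from 11% to 2.7%. Duration of response and time to response use confirmed responders only (SAP Sections 15.1.5 and 15.1.6). Up to five targets, non-target lesions and new lesions also count.
- *Rewording changes no one's entry.* Correct: Amendment 10 records enrolment as complete.

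A reader might go further and infer that the trial's response and progression results are measurement noise, or that noise alone would produce roughly the 10% null response rate. The documents support neither. The 11% is conditional on a sole target of about 5 mm and an assumed SD, whereas the 10% null is a rate for a whole cohort; noise would approach it only if nearly every patient were of that kind.

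**Conclusion.** The wording defect is real and appears in both places. Read literally, the minimum lesion size falls below 10 mm for any slice thinner than 5 mm, no floor is given, and one such lesion is enough.

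Its effect on the results is not known and may be nil, because slice thickness, reader error and the number of patients with only small targets are all missing from the documents. Where such patients exist, PFS and unconfirmed response are the exposed outcomes, and confirmed ORR much less so. At an equal SD of 1 mm, false progression at one scan for an unchanged sole target is about 26% at 5 mm against 10% at 10 mm, and false unconfirmed response about 11% against 0.7%. Under error proportional to slice thickness these differences vanish.

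No sample-size or power figure is affected. The primary endpoints, DLTs and adverse events, do not use lesion size.

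**What to change.** 1. In the Synopsis and in Section 6.1, replace *not 5 mm thick* with *thicker than 5 mm*. Ten millimetres is then the floor, the slice clause can only raise it, and the sub-bullet can be reconciled with the RECIST 1.1 sentence above it. This corrects the record and any reuse of the text.
2. In the SAP, add a listing of subjects whose only baseline target lesions are non-nodal and below 10 mm. Repeat ORR (confirmed and unconfirmed) and PFS without them. With enrolment complete, this is the part that can still change a conclusion. If the listing is empty, one sentence closes the matter.

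The cost is small. The SAP already summarises the baseline sum of target diameters (Section 7) and lists target lesions at all assessments (Listing 16.02.02.01), so no new data are needed. The downside is a little extra analysis and, under the reworded rule, the ineligibility of a few patients whose only lesions are below 10 mm.

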### Exclusion Criteria:

Document Name: GCT1021-01 Protocol

Document Number: TMF-03326

Version: 11.0

If any of the following applies, the patient MUST NOT enter the trial:

#### Hematological

1. Acute deep vein thrombosis or clinically relevant pulmonary embolism, not stable for at least 4 weeks prior to first enapotamab vedotin administration.
2. Patient has a history of thromboembolic event(s) and is not willing to take thromboembolic prophylaxis.

#### Cardiovascular

3. Have clinically significant cardiac disease, including:
  - Onset of unstable angina within 6 months of signing the Informed Consent Form (ICF).
  - Acute myocardial infarction within 6 months of the signing the ICF.
  - Known congestive heart failure (Grade III or IV as classified by the New York Heart Association); and/ or a known decreased cardiac ejection fraction of < 45% and/or baseline QT interval as corrected by Fridericia's formula (QTcF) > 480 msec or uncontrolled atrial fibrillation.
  - Uncontrolled hypertension defined as systolic blood pressure  $\geq 160$  mmHg and/or diastolic blood pressure  $\geq 100$  mmHg, despite optimal medical management.

#### Immunological

4. Ongoing or recent (within 1 year) evidence of significant autoimmune disease that required treatment with systemic immunosuppressive treatments, which may suggest risk for immune related adverse events.
5. Patients with a history of Grade 3 or higher immune related adverse events should be excluded (adverse events below Grade 3 should be discussed with the sponsor).
6. Patients with a history of non-infections pneumonitis related to prior systemic treatment and that required treatment with steroids within the last 6 months prior to enrolment.
  - If an event of pneumonitis is considered fully resolved more than 6 months prior to trial start, i.e., patient has no radiologic evidence of pneumonitis, is asymptomatic and does not require any steroid treatment, patient can be enrolled.

#### Excluded medications or treatment regimens

7. Have received granulocyte colony stimulating factor (G-CSF) or granulocyte/macrophage colony stimulating factor support 3 weeks prior to first enapotamab vedotin administration.

Document Name: GCT1021-01 Protocol

Document Number: TMF-03326

Version: 11.0

8. Have received a cumulative dose of corticosteroid > 150 mg prednisone (or equivalent doses of corticosteroids) within two weeks before the first enapotamab vedotin administration.
9. History of  $\geq$  Grade 3 allergic reactions to monoclonal antibody therapy as well as known or suspected allergy or intolerance to any agent given in the course of this trial.

#### Surgery/procedures

10. Major surgery within 4 weeks before first enapotamab vedotin administration.

#### Central nervous system

11. Any history of intracerebral arteriovenous malformation, cerebral aneurysm, brain metastases or stroke.
  - Transient ischemic attack  $\geq$  6 months prior to screening is allowed.
  - Patients with known or suspected central nervous system metastases must undergo a Computed Tomography (CT) scan or Magnetic Resonance Imaging (MRI) of the brain and/or spinal cord for documentation of baseline disease status. Spinal cord metastasis is acceptable. However, patients with known spinal cord compression that is symptomatic or patients who have not undergone definitive treatment for the spinal cord compression and subsequently do not have evidence of clinically stable disease (SD) for at least 28 days should be excluded.
  - In the expansion cohorts the enrolment of patients with stable brain metastases, i.e. being asymptomatic for the last 14 days prior to treatment initiation, is allowed (use of corticosteroids and radiotherapy are described in exclusion criterion 7)
  - Symptomatic uncontrolled brain or leptomeningeal metastases. (To be considered “controlled,” central nervous system [CNS] disease must have undergone treatment [e.g., radiation or chemotherapy] at least 2 weeks prior to first enapotamab vedotin administration. The patient must not have any new or progressive signs or symptoms related to the CNS disease and must be taking  $\leq$  10mg of prednisone or equivalent per day or no steroids). Patients who have untreated brain metastases and who are not symptomatic may enroll if the investigator feels that treatment of these metastases is not indicated. Patients with spinal cord compression may be considered for enrolment if they have received definitive treatment for this and evidence of clinically stable disease (SD) for at least 28 days.

Document Name: GCT1021-01 Protocol

Document Number: TMF-03326

Version: 11.0

#### Prior therapy

12. Any anticancer therapy including; small molecules, immunotherapy, chemotherapy monoclonal antibodies or any other experimental drug within 5 half-lives but maximum 4 weeks before first infusion. Accepted exceptions are bisphosphonates, denosumab and gonadotropin-releasing hormone agonist or antagonist, which can be continued throughout the trial.
  - Toxic effects of prior anti-cancer therapy considered as chronic, such as chemotherapy-induced fatigue, alopecia, or anorexia of  $\leq$  Grade 2, where no more resolution is expected, does not prevent the patient from participation in the trial.
13. Any prior therapy with a conjugated or unconjugated auristatin derivative/vinca-binding site targeting payload. (Previous treatment with vinca alkaloids is allowed in line with inclusion criterion #1.)
14. Radiotherapy within 14 days prior to first enapotamab vedotin administration (Palliative radiotherapy will be allowed).
15. Patients who discontinued treatment due to disease progression within the first 6 weeks of commencing a prior immune checkpoint inhibitor containing treatment

#### Other cancer/metastases

16. Known past or current malignancy other than inclusion diagnosis, except for:
  - Cervical carcinoma of Stage 1B or less.
  - Non-invasive basal cell or squamous cell skin carcinoma.
  - Non-invasive, superficial bladder cancer.
  - Prostate cancer with a current PSA level  $< 0.1$  ng/mL.
  - Breast cancer in BRCA1 or BRCA2 positive ovarian cancer patients.
  - Any curable cancer with a complete response (CR) of  $> 2$  years duration.

#### Other

17. Melanoma patients with an LDH  $\geq 3$  x ULN.
18. Ongoing significant, uncontrolled medical condition including:
  - Serious, non-healing wound, skin ulcer (of any grade), or bone fracture.
19. Presence of  $\geq$  Grade 2 peripheral neuropathy.
20. Clinically significant active viral, bacterial or fungal infection requiring:
  - Intravenous treatment with anti-infective therapy that has been administered less than two weeks prior to first dose, or

Document Name: GCT1021-01 Protocol

Document Number: TMF-03326

Version: 11.0

- Oral treatment with anti-infective therapy that has been administered less than one week prior to first dose.
  - Prophylactic anti-infective therapy, which is given without clinical symptomatic is allowed (e.g., antibiotic prophylaxis prior to dental extraction, etc.).
21. Known human immunodeficiency virus seropositivity.
22. Known history / positive serology for hepatitis B (unless immune due to vaccination or resolved natural infection or unless passive immunization due to immunoglobulin therapy):
- Positive test for antibodies to hepatitis B core antigens (anti-HBc)  
